6.2 Randomization

A participant's randomization assignment will be computer generated and provided to the HVTN CRS pharmacist through a Web-based randomization system. The randomization will be done in blocks to ensure balance across arms in Part A and in each Group in Part B. The randomization will be stratified by gender. At each institution, the pharmacist with primary responsibility for dispensing study products is charged with maintaining security of the treatment assignments (except in emergency situations as specified in the HVTN MOP).

6.3 Blinding

Participants and site staff (except for site pharmacists) will be blinded as to participant treatment arm assignments (eg, vaccine or placebo). Study product assignments are accessible to those HVTN CRS pharmacists, DAIDS protocol pharmacists and contract monitors, and SDMC staff who are required to know this information in order to ensure proper trial conduct. Any discussion of study product assignment between pharmacy staff and any other HVTN CRS staff is prohibited. The HVTN SMB members also are unblinded to treatment assignment in order to conduct review of trial safety.

Part A will be unblinded independently of Part B. Unblinding need not await completion of health contacts, which are not considered part of the "main study."

When a participant leaves the trial prior to study completion, the participant will be told he or she must wait until all participants in that part of the study (A or B) are unblinded to learn his or her treatment assignment.

Emergency unblinding decisions will be made by the site investigator. If time permits, the HVTN 124 PSRT should be consulted before emergency unblinding occurs.

6.4 Statistical analyses

This section describes the final study analyses, unblinded as to treatment arm assignment. All data from enrolled participants will be analyzed according to the initial randomization assignment regardless of how many vaccinations they received. In the rare instance that a participant receives the wrong treatment at a specific vaccination time, the Statistical Analysis Plan (SAP) will address how to analyze the participant's safety data. Analyses are modified intent-to-treat in that individuals who are randomized but not enrolled do not contribute data and hence are excluded. Because of blinding and the brief length of time between randomization and enrollment—typically no more than 4 working days—very few such individuals are expected.

Analyses for primary endpoints will be performed using SAS and R. All other descriptive and inferential statistical analyses will be performed using SAS, StatXact, or R statistical software.

No formal multiple comparison adjustments will be employed for multiple safety endpoints, multiple primary immunogenicity endpoints, or secondary endpoints. However, multiplicity adjustments will be made for certain immunogenicity assays, as discussed below, when the assay endpoint is viewed as a collection of hypotheses (eg, testing multiple peptide pools to determine a positive response).

6.4.1 Analysis variables

The analysis variables consist of baseline participant characteristics, safety, and immunogenicity for primary- and secondary-objective analyses.

6.4.2 Baseline comparability

Treatment arms will be compared for baseline participant characteristics using descriptive statistics.

6.4.3 Safety/tolerability analysis

Since enrollment is concurrent with receiving the first vaccination, all participants will have received at least 1 vaccination and therefore will provide some safety data.

6.4.3.1 Reactogenicity

The number and percentage of participants experiencing each type of reactogenicity sign or symptom will be tabulated by severity and treatment arm and the percentages displayed graphically by arm. For a given sign or symptom, each participant's reactogenicity will be counted once under the maximum severity for all injection visits. In addition, to the individual types of events, the maximum severity of local pain or tenderness, induration or erythema, and of systemic symptoms will be calculated. Wilcoxon rank sum tests will be used to test for differences in severity between arms.

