9.11 Assessments of reactogenicity

For all participants, baseline assessments are performed before and reactogenicity assessments are performed after each vaccination. All reactogenicity symptoms are followed until resolution and graded according to the Division of AIDS Table for Grading the Severity of Adult and Pediatric Adverse Events, Corrected Version 2.1, July 2017, except as noted in Section 11.2.2.

The reactogenicity assessment period is 7 full days following each vaccination per the assessment schedule shown in [Table 9-1](#). Participants are instructed to record symptoms using a postvaccination memory tool. Contacts between the participant and the site staff should take place daily between 1-3 days postvaccination for the

collection of reactogenicity data, and for events that arise during the period between vaccination and the next scheduled visit. In general, a participant who self-reports any postvaccination reaction greater than mild is seen by a clinician within 48 hours after onset, unless the reaction is improving and/or has completely resolved. Clinic staff will follow new or unresolved reactogenicity symptoms present at day 7 to resolution.

Reactogenicity events are reported using CRFs that correspond to the time of assessment in [Table 9-1](#). Reactogenicity assessments include assessments of systemic and local symptoms, vaccine-related lesions, and lymph nodes. Events not listed on a CRF, or with an onset after the reactogenicity assessment period (day of vaccination and 7 full days after), or those meeting SAE/adverse events requiring expedited reporting to DAIDS criteria, are recorded on an adverse experience log form.

Table 9-1 Schedule of reactogenicity assessments

Day	Time	Performed by
0 ^a	Baseline: before vaccination	HVTN CRS staff
	Early: 25-60 minutes after vaccination	HVTN CRS staff
	Between early assessment and 11:59pm day 0	HVTN CRS staff or participant
1-7 ^b	Between 12:00am and 11:59pm on the respective day	HVTN CRS staff or participant

^a Day of vaccination

^b New or unresolved reactogenicity symptoms present on day 7 are followed until resolution

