11.4 Safety pause and prompt PSRT AE review

When a trial is placed on safety pause, all enrollment and vaccination with the product related to the event that triggered the pause will be held until further notice. The AEs that will lead to a safety pause or prompt HVTN 124 PSRT AE review are summarized in [Table 11-1](#). Vaccinations may be suspended for safety concerns other than those described in the table, or before pause rules are met, if, in the judgment of the HVTN 124 PSRT, participant safety may be threatened. Criteria for an individual participant's departure from the schedule of vaccinations are listed in Section [7.3](#).

Table 11-1 AE notification and safety pause/AE review rules

Event and relationship to study products	Severity	HVTN CRS action ^a	HVTN Core action
SAE, related	Grade 5 or Grade 4	Phone immediately, email and submit forms immediately	Immediate pause
SAE, not related	Grade 5	Phone immediately, email and submit forms immediately	Immediate HVTN 124 PSRT notification
SAE, related	Grade 3	Email and submit forms immediately	Immediate HVTN 124 PSRT notification and prompt HVTN 124 PSRT AE review to consider pause
AE ^b , related	Grade 4 or 3	Email and submit forms immediately	Immediate HVTN 124 PSRT notification and prompt HVTN 124 PSRT AE review to consider pause
Vasculitis, related	Any grade	Phone immediately, email and submit forms immediately	Immediate pause
DTH responses, related	Any grade	Email and submit forms immediately	Prompt HVTN 124 PSRT notification and AE review to consider pause

^a Phone numbers and email addresses are found on the Protocol home page on the HVTN Members' site (<https://members.hvtn.org/protocols/hvtn124>).

^b Does not include subjective reactogenicity symptoms (injection site pain, tenderness, fatigue/malaise, myalgia, arthralgia, chills, headache, nausea).

For all safety pauses, HVTN Core notifies the HVTN 124 PSRT, HVTN Regulatory Affairs, DAIDS Pharmaceutical Affairs Branch (PAB), DAIDS Regulatory Affairs Branch (RAB), DAIDS Safety and Pharmacovigilance Team (SPT), and participating HVTN CRSs. When an immediate safety pause is triggered, HVTN Core notifies the SMB.

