9 SAFETY TABLES AND FIGURES

9.1 List of Tables

SMB reports and Safety FSRs include the following tables.

- Enrollment Report
- Demographics and Vaccination Frequencies
- Overall Protocol Status
- Maximum Local and Systemic Reactogenicity Summaries
- Adverse Experiences by Body System and Severity – By Decreasing Frequency
- Adverse Experiences by Preferred Term and Severity – By Decreasing Frequency – Includes Severe, Life-threatening or Fatal Events Only
- Adverse Experiences by Preferred Term and Severity – By Decreasing Frequency – Includes Events of All Severities
- Adverse Experiences by Preferred Term and Severity – By Decreasing Frequency – Includes Related Events Only
- Adverse Experiences by Preferred Term and Relationship to Study Product – By Decreasing Frequency – Includes Events of Any Relationship
- Expedited Adverse Experiences (EAEs) Reported to the Regulatory Support Center (RSC)
- Pregnancy Listing
- AEs of Special Interest (AESI)
- Summary of Adherence to Pause Rules
- Summary of Immediate/Prompt PSRT AE Reviews

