9.2 Participant Listings

The following listings of participant-level data are included in the SMB reports.

- Discontinuations
- Pregnancies
- Severe or Life-Threatening Local and Systemic Reactogenicities
- Moderate or Severe Erythema and Induration
- Expedited Adverse Experiences (EAEs)
- Adverse Experiences of Special Interest (AESIs)
- Severe, Life-Threatening, or Fatal Adverse Experiences
- Adverse Experiences with Relationship to Study Product (Grade 2 or higher)
- HIV Infection Results from Lab and Reported by Site
- Study Product Administration Errors

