9.3 List of Graphs

- Maximum Local Reactogenicities
- Maximum Systemic Reactogenicities
- Boxplots for Alkaline Phosphatase, AST, ALT, Creatinine, WBC, Hemoglobin, Platelets, Lymphocyte Count, and Neutrophil Count.

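### The planned reactogenicity summaries can bound but not estimate reactions to DNA given alone, because each Group 2 participant is counted once at the worst grade over DNA-only and protein visits together

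*Protocol*

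**What the plan says.** **Counting rule.** Protocol 6.4.3.1, repeated in SAP 8.3.1, tabulates and graphs reactogenicity by severity and treatment arm. For a given sign or symptom, each participant's "reactogenicity will be counted once under the maximum severity for all injection visits".

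**Planned outputs.** SAP 9.1 has one reactogenicity table entry, "Maximum Local and Systemic Reactogenicity Summaries". SAP 9.3 lists "Maximum Local Reactogenicities" and the systemic equivalent. None is split by visit, product phase or injection side. Laboratory values, by contrast, are shown by arm and visit (SAP 8.3.3).

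**Who receives DNA without protein.** Only Group 2, at Months 0, 1 and 3, with saline in the other deltoid. The same participants receive protein/GLA-SE at Months 6 and 8 (Protocol Table 3-1 and 8.1).

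**What is promised.** The primary objective (Protocol 5.1) includes the safety of the products given singly, and reactogenicity is in the first primary endpoint. Protocol 4.4.1 says Part B will evaluate the DNA prime on its own as well as in combination.

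**Other routes for these events.**
- SAP 9.1 includes expedited events, AESI, pause-rule adherence and a "Summary of Immediate/Prompt PSRT AE Reviews".
- SAP 9.2, stated for SMB reports, lists "Severe or Life-Threatening Local and Systemic Reactogenicities" and moderate or severe erythema and induration.
- Protocol 9.11 sends to the AE log only "Events not listed on a CRF, or with an onset after the reactogenicity assessment period", or those meeting SAE or expedited-reporting criteria.
- Footnote b of Protocol Table 11-1, on the row for related grade 3-4 AEs, reads "Does not include subjective reactogenicity symptoms".

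**The concern.** Protein alone has its own row, because Group 1 active participants receive nothing else. DNA alone has none. A Group 2 participant with a moderate reaction after DNA and one with the same reaction after protein land in the same cell. The report can then describe the prime-boost series but not its DNA component.

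The AE tables do not fill the gap: a solicited symptom starting within the 7-day window stays on the reactogenicity form unless it is serious or expedited, and the AE tables are by arm, not phase. What is left without a product-specific summary is mainly grade 1-2 pain or tenderness, grade 1-2 systemic symptoms including fever, and mild erythema or induration.

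The protocol's background shows why such events matter. In the predecessor trial, with a different product and dose, the only grade 2 fever reported followed a second DNA vaccination (Protocol 4.8.1). The same event in Group 2 would appear in the worst-grade table with no sign of which product preceded it.

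**Working it through.** **Inputs.** 21 active participants in Group 2; 3 DNA-only and 2 protein visits each (Protocol Table 3-1); two-sided 95% score intervals, the method behind Protocol Table 6-2.

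**1. Reproduce the plan's precision.** With p = x/n, n = 21 and z = 1.96, the interval is [p + z²/(2n) ± z√(p(1−p)/n + z²/(4n²))] / (1 + z²/n). For 0/21 the upper limit reduces to z²/(n + z²) = 3.8416/24.8416 = 15.5%. The formula also gives 0.8 to 22.7% for 1/21 and 2.7 to 28.9% for 2/21. All three agree with Table 6-2.

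**2. Exposure merged.** DNA-only visits 21 × 3 = 63; protein visits 21 × 2 = 42; total 105; 63/105 = 60%.

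**3. What the Group 2 row tells about DNA.** Suppose k of 21 participants reach a given grade or worse over all visits. Each of the k had the reaction in the DNA phase, the protein phase or both; the other 21 − k had it in neither. The DNA-phase count is therefore at most k and can be as low as 0. No event rates need to be assumed.

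| k | Interval if all k had it in the DNA phase | Interval if none did | Overlap? |
|---|---|---|---|
| 0 | 0 to 15.5% | 0 to 15.5% | identical |
| 2 | 2.7 to 28.9% | 0 to 15.5% | yes |
| 6 | 13.8 to 50.0% | 0 to 15.5% | yes |
| 7 | 17.2 to 54.6% | 0 to 15.5% | no |
| 9 | 24.5 to 63.5% | 0 to 15.5% | no |

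For 9/21: centre (0.4286 + 0.0915)/1.1829 = 0.4396; half-width 1.96 × √(0.01166 + 0.00218)/1.1829 = 0.1949; hence 24.5 to 63.5%. For 7/21: centre 0.3591, half-width 0.1872; hence 17.2 to 54.6%.

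**4. Illustration with assumed rates.** The documents give no phase-specific rates, so these are assumptions. Let pD be a participant's chance of the reaction over the DNA visits and pP over the protein visits. If the two are independent, the worst-grade rate is 1 − (1 − pD)(1 − pP).
- pP = 10%: raising pD from 5% to 20% moves the reported rate from 14.5% to 28%.
- pP = 30%: from 33.5% to 44%.
- pP = 50%: from 52.5% to 60%.

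The more reactogenic the protein phase, the less the reported rate responds to DNA. In the last case a fourfold change in pD moves it by 7.5 percentage points.

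**The case against.** **The SMB will see DNA-only data.** The SAP 9.1 tables also go into SMB reports about every 4 months, and Group 2 receives no protein before Day 168. A cut before then would show only DNA visits for Group 2. This is true, but it depends on timing. Part B opens with only 10 participants across both groups, so such a cut may cover part of the arm, and later cumulative reports and the final report merge the phases again.

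**The arms separate the products.** DNA or its placebo goes in the left deltoid and protein or its placebo in the right, unless contraindicated. If local reactions are recorded by side, most could be attributed. No table by side is planned, however, and side cannot separate systemic symptoms.

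**Group 1 gives context.** It shows two doses of the same protein/GLA-SE without DNA. With 10 active participants, not randomised against Group 2, it is context and not a basis for an estimate.

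**The remaining gap is narrow.** This stands in part. Severe and serious events are mostly covered elsewhere, and worst grade per participant is a coherent summary of each regimen's tolerability. Non-overlap from k = 7 is a descriptive marker chosen here; the plan sets no such standard. The objective nevertheless names the products singly as well as the regimens, and listings without denominators give no rates.

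**Conclusion.** The concern holds. Followed exactly, the plan gives an upper bound on mild-to-moderate reactogenicity of DNA alone and no estimate of it, for a component of the first primary endpoint that the protocol says it will evaluate. The loss is largest for common reactions: from 7 of 21 upward, the Group 2 row fits DNA-phase rates whose 95% intervals do not overlap. It is small for rare severe reactions and nil when the count is 0.

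The bound rests only on the counting rule and the schema; the illustration in step 4 is the only part that uses assumed rates. No planned test or interval is wrong and no data are lost. The output should be specified before the final analysis, not left to an ad hoc request.

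**What to change.** Keep the worst-grade table and its Wilcoxon test. Add to SAP 8.3.1, 9.1 and 9.3 descriptive tables and one graph, with no new tests, giving for Group 2 the maximum grade over Months 0, 1 and 3 and, separately, over Months 6 and 8. The denominator is the participants vaccinated in that phase. Because enrollment coincides with the first vaccination, the DNA-phase denominator should be all 21, so the precision in Table 6-2 applies directly. Reactogenicity by arm and vaccination visit would serve equally well.

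When the phase labels are written, SAP 10.1, which describes the Group 2 boosts as DNA plus protein, must be reconciled with the schema in SAP section 2 and with Protocol 8.1, which show protein plus placebo.

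The cost is SAP wording and programming. Protocol 9.11 already provides that reactogenicity "assessments are performed after each vaccination", and SAP section 1 schedules a review of the SAP before the final analysis. Design, data collection and clinical rules are unchanged.

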6.4.3.2 AEs and SAEs

AEs will be summarized using MedDRA System Organ Class and preferred terms. Tables will show by treatment arm the number and percentage of participants experiencing an AE within a System Organ Class or within preferred term category by severity or by relationship to study product. For the calculations in these tables, a participant with multiple AEs within a category will be counted once under the maximum severity or the strongest recorded causal relationship to study product. Formal statistical testing comparing arms is not planned since interpretation of differences must rely heavily upon clinical judgment.

A listing of SAEs reported to the DAIDS Regulatory Support Center (RSC) Safety Office will provide details of the events including severity, relationship to study product, time between onset and last vaccination, and number of vaccinations received. A separate listing will do the same for AEs of special interest (AESI). AESI for this protocol include but are not limited to autoimmune disorders; a sample list of AESI is provided in [Appendix L](#).

6.4.3.3 Local laboratory values

Box plots of local laboratory values will be generated for baseline values and for values measured during the course of the study by treatment arm and visit. Each box plot will show the first quartile, the median, and the third quartile. Outliers (values outside the box plot) will also be plotted. If appropriate, horizontal lines representing boundaries for abnormal values will be plotted.

For each local laboratory measure, summary statistics will be presented by treatment arm and timepoint, as well as changes from baseline for postenrollment values. In addition, the number (percentage) of participants with local laboratory values recorded as meeting Grade 1 AE criteria or above as specified in the Division of AIDS Table for Grading the Severity of Adult and Pediatric Adverse Events (see section [9.11](#)) will be tabulated by treatment arm for each postvaccination timepoint. Reportable clinical laboratory abnormalities without an associated clinical diagnosis will also be included in the tabulation of AEs described above.

6.4.3.4 Reasons for vaccination discontinuation and early study termination

The number and percentage of participants who discontinue vaccination and who terminate the study early will be tabulated by reason and treatment arm.

6.4.4 Immunogenicity analysis

6.4.4.1 General approach

For the statistical analysis of immunogenicity endpoints, data from enrolled participants will be used according to the initial randomization assignment regardless of how many injections they received. Additional analyses may be performed, limited to participants who received all scheduled injections per

protocol. Assay results that are unreliable, from specimens collected outside of the visit window, or from HIV-infected participants post infection are excluded. Since the exact date of HIV infection is unknown, any assay data from blood draws 4 weeks prior to an infected participant's last seronegative sample and thereafter may be excluded. If an HIV-infected participant does not have a seronegative sample post enrollment, then all data from that participant may be excluded from the analysis.

Discrete categorical assay endpoints (eg, response rates) will be analyzed by tabulating the frequency of positive response for each assay by antigen and treatment arm at each timepoint for which an assessment is performed. Crude response rates will be presented with their corresponding 95% confidence interval estimates calculated using the score test method (52). Because of the small numbers of control participants in each group, no adjustment will be made to the vaccine arm estimates for the false positive rates in the control arms. Barnard or Fisher's exact tests, as specified in the SAP, will be used to compare the response rates of any 2 vaccine arms, with a significant difference declared if the 2-sided p-value is ≤ 0.05 . In general Barnard's is preferred since under most circumstances it is more powerful than Fisher's (54).

In addition to response rate estimates for each timepoint, the probability of observing at least 1 positive response by a given timepoint and the probability of observing more than 1 positive response by a given timepoint will be estimated, with corresponding confidence intervals, for each vaccine arm using maximum likelihood-based methods (55).

For quantitative assay data (eg, IgG binding Ab response from BAMA or percentage of positive cells from the ICS assay), graphical and tabular summaries of the distributions by antigen, treatment arm, and timepoint will be made. For all primary and secondary immunogenicity endpoints, box plots and plots of estimated reverse cumulative distribution curves will be used for graphical display of all of the study arms. Typically the results will be shown for each vaccine arm and for the set of placebo arms pooled into one group.

The difference between arms at a specific timepoint will be tested with a nonparametric Wilcoxon rank sum test if the data are not normally distributed and with a 2-sample t-test if the data appear to be normally distributed.

Some immunologic assays have underlying continuous or count-type readout that are dichotomized into responder/nonresponder categories (eg, ICS). If treatment arm differences for these assays are best summarized by a mixture model, then either Lachenbruch's test statistic (56) or an alternative two-part test (57) (as defined in the SAP) will be used to evaluate the composite null hypothesis of equal response rates in the 2 arms and equal response distributions.

Lachenbruch's test statistic equals the square of a binomial Z-statistic for comparing the response rates plus the square of a Wilcoxon statistic for comparing the response distributions in the subgroup of responders. A permutation procedure is used to obtain a 2-sided p-value. For estimation,

differences in response rates between arms will be estimated using the methods described above, and in the subgroup of positive responders, differences in location parameters between arms will be estimated using the methods described above.

More sophisticated analyses employing repeated measures methodology (for example, linear mixed models or marginal mean models fit by generalized estimating equations) may be utilized to incorporate immune responses over several timepoints and to test for differences over time. However, inference from such analyses would be limited by the small sample size of this study. All statistical tests will be 2-sided and will be considered statistically significant if $p \leq 0.05$.

Based upon previous HVTN trials, missing 10-15% of immunogenicity results for a specific assay is common due to study participants terminating from the study early, problems in shipping specimens, or low cell viability of processed peripheral blood mononuclear cells (PBMCs). To achieve unbiased statistical estimation and inferences with standard methods applied in a complete-case manner (only including participants with observed data in the analysis), missing data need to be missing completely at random (MCAR). Following the most commonly used definition, MCAR assumes that the probability of an observation being missing does not depend on any participant characteristics (observed or unobserved). When missing data are minimal (specifically if no more than 20% of participants are missing any values), then standard complete-case methods will be used, because violations of the MCAR assumption will have little impact on the estimates and hypothesis tests.

If a substantial amount of immunogenicity data are missing for an endpoint (at least 1 value missing from more than 20% of participants), then using the methods that require the MCAR assumption may give misleading results. In this situation, analyses of the immunogenicity endpoints at a specific timepoint will be performed using parametric generalized linear models fit by maximum likelihood. These methods provide unbiased estimation and inferences under the parametric modeling assumptions and the assumption that the missing data are missing at random (MAR). MAR assumes that the probability of an observation being missing may depend upon the observed responses and upon observed covariates, but not upon any unobserved factors. Generalized linear models for response rates will use a binomial error distribution and for quantitative endpoints, a normal error distribution. For assessing repeated immunogenicity measurement, linear mixed effects models will be used. If the immunological outcomes are left- and/or right-censored, then the linear mixed effects models of Hughes (58) will be used, because they accommodate the censoring. In addition, secondary analyses of repeated immunogenicity measurements may be done using weighted GEE (59) methods, which are valid under MAR. All of the models described above in this paragraph will include as covariates all available baseline predictors of the missing outcomes.

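### Above 20% missing, the single-timepoint GLM is called unbiased under MAR, but it is valid only when missingness depends on arm and the included baseline covariates

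*Protocol*

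**What the plan says.** The missing-data text in Protocol 6.4.4.1 has two branches, and SAP 8.4.1 repeats it.

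- Complete-case methods are used when missing data are minimal, "specifically if no more than 20% of participants are missing any values".
- The other branch applies when there is "at least 1 value missing from more than 20% of participants". There, "analyses of the immunogenicity endpoints at a specific timepoint will be performed using parametric generalized linear models fit by maximum likelihood".

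The property claimed for the second branch follows at once: "These methods provide unbiased estimation and inferences under the parametric modeling assumptions and the assumption that the missing data are missing at random (MAR"). The definition comes next: "MAR assumes that the probability of an observation being missing may depend upon the observed responses and upon observed covariates", but not on unobserved factors. On covariates, the models "will include as covariates all available baseline predictors of the missing outcomes".

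The same paragraph has a separate sentence for longitudinal data: "For assessing repeated immunogenicity measurement, linear mixed effects models will be used". It adds a censored version and allows weighted GEE as a secondary analysis. Neither is assigned to the T2-T3 comparison at the primary timepoint. SAP 10.1 to 10.4 compare T2 with T3 within timepoint by Barnard, Wilcoxon or t-tests and name no baseline predictors.

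**The concern.** The stated property and the stated model do not match. The definition of MAR allows missingness to depend on responses already observed. The single-timepoint GLM contains the outcome at that timepoint, arm and baseline covariates, and nothing else. If a participant's month 8.5 value is missing for a reason linked to an earlier measured response, or to reactogenicity recorded after vaccination, the plan's MAR holds but the model does not condition on what makes it hold.

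At stake are the month 8.5 T2-T3 contrast and the arm-level estimates. The arm estimates matter in their own right, because Protocol 6.4.4.3 ranks the regimens on estimated mean AUC-MB. A report could describe an estimate as unbiased under MAR when the assumption actually needed is narrower.

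**Working it through.** **What the likelihood contains.** With one outcome per participant, the GLM likelihood is the product of f(y | arm, x) over participants. For a participant with y missing, the term integrates to 1 and drops out. The fit is therefore a covariate-adjusted complete-case analysis. It is valid if P(missing | arm, x, y) = P(missing | arm, x). If missingness also depends on an earlier response R, and R predicts y given arm and x, that condition fails even though the plan's MAR is met.

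**The plan's own figure.** Protocol 6.1 and 6.1.2 enrol 21 vaccinees per Part B arm and allow 15% missing: 21 × 0.85 = 17.85, or 18 as stated.

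**How often the rule applies.** More than 20% of 48 is 10 or more (0.20 × 48 = 9.6). At a uniform 15% missing rate, P(X ≥ 10) = 0.174. For the 42 vaccinees alone, P(X ≥ 9) = 0.169. At 10% missing it is about 2%. These rates assume uniform missingness and should not be multiplied by the biases below, which assume heavier loss in one arm or overall.

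**Size without covariates.** None of these inputs is in the documents. Let R correlate ρ with the month 8.5 outcome (SD 1). T3 participants above the median of R are missing with probability p; those below, with probability 0.1. T2 losses are unrelated to R. The mean of R in the upper or lower half of a standard normal is ±0.798, so the bias in the T3 mean is

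0.798 × ρ × [(1 − p) − 0.9] / [(1 − p) + 0.9].

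- p = 0.5: 0.798 × (−0.4/1.4) = −0.228, which gives −0.07 at ρ = 0.3 and −0.16 at ρ = 0.7. T3 is 30% missing; with T2 at 15%, overall 22.5%.
- p = 0.7: 0.798 × (−0.6/1.2) = −0.399, which gives −0.12 and −0.28. T3 is 40% missing; with T2 at 10%, overall 25%.

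**Size with a baseline covariate, as the plan requires.** Simulation at 21 per arm, restricted to datasets with more than 20% missing, gave a bias of 0.06 to 0.26 SD and a false-positive rate of 5.8 to 10.4% when the covariate is weak. With a strong covariate the bias was at most 0.06 SD and the error about 5%. As a rough check, a covariate correlated c with R removes about c² of the bias. At c = 0.3, 0.28 × (1 − 0.09) = 0.25. At c = 0.9, 0.28 × (1 − 0.81) = 0.05.

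**A second missingness model.** Here the log-odds of missing change by 1.5 per SD of R in one arm only, and the baseline correlation is 0.3. Absolute large-sample bias in the T2-T3 difference, in SD:

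| Missing | ρ | Complete case | GLM | Joint likelihood using R |
|---|---|---|---|---|
| 25% | 0.3 / 0.5 / 0.7 | 0.08 / 0.14 / 0.19 | 0.08 / 0.13 / 0.18 | about 0 |
| 35% | 0.3 / 0.5 / 0.7 | 0.11 / 0.19 / 0.26 | 0.10 / 0.18 / 0.24 | about 0 |

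At ρ = 0.7 with a baseline predictor correlated 0.9 with R, the GLM bias falls to 0.04 to 0.05.

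**Where the GLM does well, and where bias cancels.**

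- Missingness driven by a baseline covariate in one arm: complete case is off by 0.05 to 0.16 SD, the GLM by about 0.
- Same dependence on R in both arms, with R equal between arms: about 0 in the difference, but the arm mean is off by 0.18 SD (25% missing) to 0.25 SD (35%).
- Same dependence, with R 1 SD apart and a true difference of 0.7 SD: the difference is understated by 0.14 to 0.16 SD.

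**The case against.** Several objections stand, and they limit the point.

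- A reader might infer that the GLM ignores all post-vaccination data and keeps all the dropout bias. It does not. It models the post-vaccination outcome at its own timepoint and removes the bias that its baseline covariates explain. What it leaves out is the other post-vaccination data.
- Earlier responses may not exist. Protocol 10.3 and SAP 10.1 to 10.4 make most assays at other post-vaccination timepoints contingent on initial results. If an earlier response was never measured, missingness driven by it falls outside the plan's MAR, and the claim is not contradicted on that account. Reactogenicity, however, is recorded after every vaccination (Protocol 9.11), and Protocol 6.4.5 foresees month 3.5 binding data.
- Where earlier responses do exist, the paragraph already names mixed models. The gap is that the month 8.5 contrast is not assigned to them.
- A reader might infer that stopping vaccination creates missing data. Protocol 7.3.3 strongly encourages such participants to stay in follow-up, and 6.4.4.1 analyses them regardless of injections received. Shipping and cell-viability losses are plausibly unrelated to response.
- Heavy loss of high responders from one arm has no source in the documents. Participants do not know their antibody levels, so loss would have to act through something like reactogenicity, whose correlation with response is not given.

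None of this makes the unbiasedness sentence correct for the single-timepoint GLM.

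**Conclusion.** The claim in Protocol 6.4.4.1 and SAP 8.4.1 is too strong for the single-timepoint GLM. The model is valid when missingness depends on arm and the included baseline covariates, which is narrower than the MAR the plan defines. This follows from the form of the likelihood and needs no assumption about this trial's data.

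The size does need assumptions. Under one-arm missingness tied to an earlier response (correlation 0.3 to 0.7, about 22 to 25% missing or more), the T2-T3 bias is about 0.06 to 0.26 SD with a weak covariate and at most about 0.06 SD with a strong one. The SAP names no covariates, so the documents do not show which case applies. The bias in the difference is near zero if the same mechanism acts equally in both arms, although the arm means are still shifted.

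A reader might go further and conclude that the T2-T3 test exceeds its 5% error rate whenever the rule is triggered. The documents do not support that: the inflation appears only under arm-differential missingness with a weak covariate. The point concerns a contingency rule for secondary endpoints in a phase 1 trial. It is worth correcting because the correction is cheap.

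**What to change.** Amend Protocol 6.4.4.1 and SAP 8.4.1 as follows.

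1. Restate the property: the single-timepoint GLM is valid when missingness depends only on arm and the included baseline covariates. Name those covariates in the SAP.
2. Above 20% missing, where earlier post-vaccination timepoints were assayed, estimate the month 8.5 T2-T3 contrast for quantitative endpoints from the linear mixed model (or its censored version) over all observed timepoints. Keep the GLM as the sensitivity analysis.
3. Where only the primary timepoint was assayed, and for response rates, keep the GLM under the restated assumption. Add a sensitivity analysis by multiple imputation or inverse-probability weighting that uses reactogenicity and vaccinations received.

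The third item should stay a sensitivity analysis, because its performance at 21 per arm has not been tested and weights or imputations may be unstable at that size. No new data are needed. The cost is SAP wording, some programming and one more model to specify.
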